## 17.0 STATISTICAL METHODOLOGY

### 17.1 Overview

The primary endpoint of this study is ORR. A response is defined as a PR or CR as a best response (or that has been confirmed). The trial will be considered to be successful if the ORR, originally achieved in similar patient populations of metastatic NSCLC treated in a protocol of Ipilimumab and local radiotherapy to a metastatic lesion, is increased by 20% or more. It is assumed that the ORR in the first-line is 40% and the ORR in the second-line is 18% and that there will be approximately 60% first-line patients and 40% second-line (and beyond) patients. This yields an historical ORR of 0.31 (= (0.60x0.40) + (0.40x0.18)). The trial design is a single arm, multi-center, Simon optimal two-stage design. Tumor responses will be assessed at baseline, at Day 70 ( $\pm$  7 days), and at specified intervals as stated in section 10.0. Patients will be evaluated for response at day 70 day  $\pm$  7 days. Patients will be enrolled in two stages with 15 patients in the first stage, and potentially an additional 29 patients in the second stage. The decision to enroll patients into the second stage will depend on the number of responses observed in the first stage.

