### **1.2.8 NYU S14-00208/ NCT02221739: Ipilimumab and local RT in chemo-refractory metastatic NSCLC**

NYU S14-00208/NCT02221739 was a single institution prospective trial that tested the hypothesis that the addition of local radiotherapy to a metastatic site in metastatic chemo-resistant NSCLC could enhance the ORR of CTLA-4 blockade by ipilimumab. Patients needed to have progressed after at least one cycle of chemotherapy. Additional eligibility criteria included measurable disease in at least 2 sites, controlled brain metastases and ECOG PS 0-2. The study was a Phase II, optimal two-stage Simon design; 10 patients were to be treated in stage 1 at 6Gy x5; if no grade  $\geq 3$  toxicities, 10 additional patients treated at 9.5Gy x3; ipilimumab 3mg/kg q3 weeks x4 infusions. If  $\geq 1$  abscopal responses in stage 1, the trial was to proceed to enroll an additional 19 patients. Primary endpoint was response per RECIST v1.1 (baseline and post treatment PET/CT) Secondary endpoint was best abscopal response, as well as immunologic biomarkers. Thirty-nine patients accrued to the trial: only 18 were able to complete treatment of radiotherapy plus 4 cycles of Ipilimumab, mostly due to the advanced ECOG score inclusion of that trial (ECOG eligibility up to 2). Based on intent to treat ORR was 18%(7/39). In addition, ORR was 33% among the 18 patients who completed treatment: there were 2 CR, 5 PR, 5 SD and 9 PD. Figure 1 shows the waterfall plot of response for the study, as measured in lesions

outside the irradiated field (abscopal response). Figure 3 demonstrates at a 1-year median follow up a survival difference between the patients who progressed versus the responders. Median survival is still not reached for CR/PR/SD versus 9 months for patients with PD (log-rank test:  $p = 0.016$ ; HR = 9.174).

[figure not shown]

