## 3.0 STUDY OBJECTIVES

### Primary objectives

- 2.1 To demonstrate safety of combining initial concurrent radiotherapy and ipilimumab as an induction regimen to the combination of Ipi/Nivo in NSCLC
- 2.2 To enhance the ORR to the combination of Ipi/Nivo in NSCLC by preceding it with a combination of Ipi/RT to convert the irradiated tumor into an in situ vaccine

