Assessment of response: Response is defined as an objective radiographic response of the measurable metastatic site(s) outside the radiation field evaluated by CT at 3 months after the start of treatment. Lesions will be measured using RECIST 1.1 [52] and best response (PR + CR) based on these criteria will be recorded. To reduce confounding, the irradiated lesion will be excluded from baseline measurement and measurement for the assessment of in-field response will be recorded separately.

**Objective 2.2:** To enhance the ORR to the combination of Ipi/Nivo in NSCLC by preceding it with a combination of Ipi/RT to convert the irradiated tumor into an in situ vaccine.

The trial is designed to enhance ORR to the combination of Ipi/Nivo, by an initial induction of Ipi/RT to one of the metastatic lesions. Since a) approximately 2/3 of chemo-refractory metastatic NSCLC cancers are expected to express  $<1\%$  PDL1; b) Checkmate 012 demonstrated a 19%

objective response rate (ORR) in these patients and c) our recent study of radiation and ipi demonstrated 18% ORR based on intent to treat, the current trial is powered to test in patients with metastatic NSCLC whether the initial addition of local radiotherapy during ipilimumab can increase the ORR to immune checkpoints independently from PD-L1 expression. In order to test this hypothesis a Simon's two-stage design is chosen for this trial, thus 15 patients will be enrolled in the first stage with an upper limit of 4 responses for 1st stage rejection of the combined regimen. If 5 or more objective responses are seen then the trial will proceed to the second stage and an additional 29 patients with PD-L1 negative tumors will be enrolled and treated, for a total target accrual of 44 evaluable patients. A patient is deemed evaluable if they have measurable disease at baseline and had a 9 week imaging evaluation. To ensure 44 evaluable patients, up to 4 additional patients will be enrolled if necessary to replace patients who withdrew or did not have a 9 week evaluation. If there are more than 44 evaluable patients, the decision rule will be made based on the first 44 evaluable patients. Patients who were replaced because they were not evaluable, will not be part of the denominator.

[figure not shown]
**Objective 2.3:** To explore whether early changes in TCR repertoire in peripheral blood are associated with response to treatment

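### The 31% null blends a first-line rate with a later-line rate from RT plus ipilimumab without nivolumab, so rejecting it does not show that RT enhances ipi/nivo; the direction of the error is uncertain

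*Combined protocol and SAP*

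**What the plan says.** Section 3.0 gives the primary efficacy objective as "To enhance the ORR to the combination of Ipi/Nivo in NSCLC by preceding it with a combination of Ipi/RT". Section 17.1 then builds the null from two rates, "It is assumed that the ORR in the first-line is 40% and the ORR in the second-line is 18" per cent, and a case mix of "approximately 60% first-line patients and 40% second-line (and beyond) patients". It concludes: "This yields an historical ORR of 0.31". The same section defines success as a 20% increase over the ORR "originally achieved in similar patient populations of metastatic NSCLC treated in a protocol of Ipilimumab and local radiotherapy to a metastatic lesion". It cites no source beside either the 40% or the 18%.

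Section 4.0 (Objective 2.2) gives 18% as the ORR of the group's earlier radiation-plus-ipilimumab study. Section 1.2.8 describes that study: chemo-refractory patients, ECOG 0-2, RT with four infusions of ipilimumab and no nivolumab. It reports "Based on intent to treat ORR was 18%(7/39". Only 18 of the 39 completed treatment, "mostly due to the advanced ECOG score inclusion of that trial (ECOG eligibility up to 2".

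The present trial takes ECOG 0-1 or Karnofsky 70% and above (section 5.1) and gives nivolumab from day 22 (section 6.0). To be evaluable, a patient needs measurable disease at baseline and a 9-week scan. Section 4.0 adds: "Patients who were replaced because they were not evaluable, will not be part of the denominator".

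**The concern.** A test of whether RT raises the ORR of ipi/nivo needs a null that estimates ipi/nivo without RT, in comparable patients and on the same denominator. The later-line component of this null has a different regimen, which already contains the RT under test and lacks nivolumab. It also comes from a population with a wider performance-status range and from an all-patients denominator.

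Two things are at stake. The first is interpretation: with 18 or more responses, a later-line contribution from RT could not be separated from the addition of nivolumab, from fitter patients or from the smaller denominator. The second is calibration: the stated type I error of 0.10 holds only if the composite rate without RT really is about 31%.

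**Working it through.** **1. The plan's own figures.** Null = 0.60 × 0.40 + 0.40 × 0.18 = 0.240 + 0.072 = 0.312, rounded in the plan to 0.31.

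The probability of declaring success at true rate p is

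P(p) = Σ (x = 5 to 15) Bin(x; 15, p) × Pr[Bin(29, p) ≥ 18 − x].

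This gives P(0.31) = 0.0946, P(0.312) = 0.0996 and P(0.51) = 0.900. A search for the Simon optimal design at 31% against 51% returns the same design: stop at 4 or fewer of 15, and reject at 18 or more of 44. Section 17.2 instead gives 17 as the cut-off; that rule has type I error 0.150 at 31%, so the stated 0.10 fits only the 18 rule. The synopsis, section 4.0 and section 17.3 (Primary analysis) also use 18, and so do the calculations below.

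**2. Later-line rate.** Hold first-line at 40% and the mix at 60/40, and let RT add nothing. With s the later-line ipi/nivo ORR without RT, null = 0.24 + 0.40 × s.

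| s | Where it comes from | Null | Type I error |
|---|---|---|---|
| 16% | anti-PD-1 alone after chemotherapy (1.2.9) | 0.304 | 0.081 |
| 18% | the plan | 0.312 | 0.100 |
| 19% | ipi/nivo, PD-L1 below 1% (4.0, Objective 2.2) | 0.316 | 0.110 |
| 20% | assumption | 0.320 | 0.121 |
| 25% | assumption | 0.340 | 0.187 |

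The error reaches 0.10 at s = 18.04%, so the design has almost no slack above 18%. The documents give no later-line ORR for ipi/nivo without RT. The 7/39 is itself imprecise, with an exact 95% interval of 7.5% to 33.5%.

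**3. Denominator, taken alone.** Suppose the ORR is 31% among all 48 accrued, and the four patients removed are all non-responders. The evaluable ORR is 0.31 × 48 / 44 = 0.338, and P(0.338) = 0.181. This affects both lines and needs no assumption about nivolumab.

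**4. The other inputs, for scale.** Section 1.2.10 gives 39% to 47% for first-line ipi/nivo.
- First-line 47%, mix 60/40, later-line 18%: null 0.354, type I error 0.244.
- First-line 40%, later-line 18%, mix 50/50: null 0.290, type I error 0.054.
- First-line 40%, later-line 18%, mix 70/30: null 0.334, type I error 0.166.

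**The case against.** A reader might infer that 18% is simply too low, because the earlier trial lacked nivolumab, admitted ECOG 2 patients and counted everyone, so that the false-positive rate must exceed 10%. The documents do not support that. The benchmark already includes RT; if RT works, this makes 18% too high as a no-RT rate. The present criteria also no longer exclude prior checkpoint blockade, which could lower response. At 16% the error is 0.081, below nominal.

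A reader might also put in the 33% reported in section 1.2.8 for patients who completed treatment. That figure cannot serve. It is again RT plus ipilimumab, and completing four infusions is not the same as having a 9-week scan. It is also inconsistent with its own counts: 2 CR + 5 PR = 7, which is 39% of 18, while the listed categories sum to 21 and 7/21 = 33%.

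In the plan's favour, section 4.0 offers 19% for ipi/nivo without RT in PD-L1-low tumours, which it expects to be about two thirds of chemo-refractory cases. That moves the error only to 0.110. It is an imperfect proxy: section 1.2.10 describes that study as first-line, and the figure is a PD-L1 subgroup.

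It can also be said that no single-arm trial isolates a component, that section 17.1 names its reference protocol openly, and that section 17.3 claims only that the strategy merits further evaluation. That is fair, but sections 1.1, 1.2.11 and 3.0 present the result as an increase in response to ipi/nivo, which this null cannot test. Finally, replacement is capped at four patients; even in the worst case of step 3 the trial would still fail about 82% of the time.

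**Conclusion.** The mismatch between null and objective stands. The 18% in section 17.1 is unsourced there, but it equals the 7/39 figure, and the same paragraph names the ipilimumab-plus-radiotherapy protocol. Rejecting the composite null would not by itself establish that RT adds to ipi/nivo in later-line patients.

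Inflation of type I error is possible but not shown. For later-line rates of 16% to 25% it runs from 0.081 to 0.187, given 40% first-line, a 60/40 mix and the 18-of-44 rule; the values above 19% have no anchor in the documents. The evaluable-only denominator can separately take it to 0.181 in its worst case. The later-line rate supplies only 0.072 of the 0.312, and plausible changes in the first-line rate or the mix matter at least as much. The sensible response is a two-sided sensitivity analysis and a narrower claim; the design can stay as it is.

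**What to change.** In section 17.1, state the source, regimen, population and denominator of each component of the null. Say that rejecting the composite does not by itself establish an RT contribution to ipi/nivo.

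In section 17.3:
- Report an all-treated ORR, with patients lacking a 9-week scan counted as non-responders, beside the evaluable-only ORR.
- Report ORR by line of therapy descriptively, with exact intervals. Do not test either line against a fixed benchmark, because the documents supply no valid one for later-line ipi/nivo. About 0.40 × 44 ≈ 18 later-line patients are expected, so the interval will be wide.
- Add a table of the result against nulls from about 0.28 to 0.36, below and above 0.31. At 60/40 with 40% first-line, those ends correspond to later-line rates of 10% and 30%, and to type I errors of 0.040 and 0.270. Include the null recomputed from the observed line mix.

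The cost is some SAP wording and one or two tables from data already collected. No extra patients or change of decision rule are needed. The price is a more modest claim.

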### 17.2 Sample size justification

As mentioned, a Simon's two-stage optimal design [65] will be used. The null hypothesis is that the true response rate is 31% will be tested against a one-sided alternative. If there are 4 or fewer responses in the first 15 patients, the study will be stopped. Otherwise 29 additional patients will be accrued for a total of 44 patients. The null hypothesis will be rejected if 17 or more responses are observed in 44 patients. This design yields a type I error of 0.10 and power of 90% when the true response rate is 51%. The target sample size is 44 evaluable patients and up to 48 patients (4 extra patients) will be accrued to account for non-evaluable patients or patients who withdraw prior to the 9-week evaluation.

### **17.3 Secondary analyses**

Progression free survival (PFS) is defined as time from study enrollment until documented disease progression or death, whichever occurs earlier. Patients who are alive at time of the data cutoff and do not have documented disease progression will be censored. Overall survival (OS) will be measured from the time of study enrollment until death from any cause. Patients alive at the time of data cutoff will be censored. The Kaplan-Meier estimator and curve will be used to summarize the PFS and OS data. Duration of response (DOR) will be measured from the time of documented response until disease progression. If a patient has not progressed at the time of data cutoff, they will be censored. Duration of response will be summarized with Kaplan-Meier incidence curves and will only include patients with a documented response (the clock starts at the time of response and the incident event is disease progression). The median DOR and corresponding 95% CI will be generated. The time to disease progression (TTP) also be estimated with K-M incidence curves. The start will be the time of study enrollment. The event will be documented disease progression. Patients who died prior to documented progression or are alive and progression free at time of data cutoff will be censored. The median TTP and corresponding 95% CI will be generated.

Changes in the gut microbiome will be assessed globally and at each individual timepoint. In the global analysis of measure of diversity, the data will be summarized by a normalized area under the curve (AUC). The AUC of responders will be compared to the AUC of non-responders using a two-group t-test (or non-parametric test if more appropriate). In addition, logistic regression will assess the relationship of the AUC for the diversity index and responder status. This model may adjust for baseline levels of diversity and other relative clinical variables. Changes in the diversity index will also be evaluated at each timepoint and compared between responders and none responders using a two-group t-test (or non-parametric test if needed). A similar analysis will be done with the changes in serum marker levels over time. A global analysis will be done using a normalized AUC and making a comparison between responders and non-responders. There will also be analyses done for changes at each timepoint between responders and non-responders. For these analysis, we will also generate graphs of the data that show the changes over time in the measurements for each individual patient (i.e. a spaghetti plot). We will superimpose a loess curves on the plot: one for the entire cohort, one for responders and one for non-responders). Given the relatively small sample size, these analyses are exploratory and no adjustment will be made for multiple comparisons.

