Criteria for Evaluation (Efficacy, safety, stopping rules, etc.)	
CLINICAL ENDPOINTS
 
Tumor Response will be evaluated using the RECIST best response (Partial Response (PR) + Complete Response (CR)). The irradiated lesion will be excluded from the assessment of response.
 
Time to progression and duration of response are also endpoints of the study.
 
IMMUNOLOGICAL ENDPOINTS
 
We propose to analyze immunological changes that reflect both local and systemic responses, and investigate both general immune activation as well as tumor antigen-specific T- and B-cell responses. Serial blood samples will be collected for serum and peripheral blood mononuclear cells (PBMC): at baseline (pre-treatment, end of radiation therapy), at the time of the first three infusions of ipilimumab, at the time of the first three infusions of nivolumab, at response evaluation (Day 70 <math>\pm</math> 7 days), and at 6 months. Small aliquots of PBMC (<math>\sim 10^6</math> cells) will be used ex vivo for preparation of DNA and RNA, and the remainder preserved frozen until evaluation by flow cytometry and/or by functional assays. In addition, Stool samples will be collected before treatment, at day 22, at Day 70 response (<math>\pm</math> 7 days) and 6 months to explore changes of the microbiome during ICB. Tissue biopsies will be obtained at baseline and at Day 22 (optional), post treatment from patients who consent to the optional biopsies.

Statistics	
A Simon's two-stage optimal design will be used. The null hypothesis is that the true response rate is 31% will be tested against a one-sided alternative. If there are 4 or fewer responses in these 15 patients, the study will be stopped. Otherwise 29 additional patients will be accrued for a total of 44 patients. The null hypothesis will be rejected if 18 or more responses are observed in 44 patients. This design yields a type I error of 0.10 and power of 90% when the true response rate is 51%. The target sample size is 44 evaluable patients and up to 48 patients will be accrued to account for non-evaluable patients or patients who withdraw prior to the 9-week evaluation.

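### Duration of response leaves out death as an event, and a Kaplan-Meier incidence curve for time to progression overstates the incidence of progression

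*Combined protocol and SAP*

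**What the plan says.** All the rules are in Section 17.3, Secondary analyses.

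- **DOR, event.** "Duration of response (DOR) will be measured from the time of documented response until disease progression". The section repeats that "the clock starts at the time of response and the incident event is disease progression".
- **DOR, censoring.** "If a patient has not progressed at the time of data cutoff, they will be censored". Death is not mentioned, and no censoring date is given for a responder who has died.
- **DOR, estimator.** "Duration of response will be summarized with Kaplan-Meier incidence curves and will only include patients with a documented response".
- **TTP.** It will "also be estimated with K-M incidence curves", starting at enrollment. The censoring rule is explicit: "Patients who died prior to documented progression or are alive and progression free at time of data cutoff will be censored".
- **PFS, for comparison.** It is "time from study enrollment until documented disease progression or death, whichever occurs earlier".

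A median with a 95% confidence interval is planned for both DOR and TTP. The synopsis gives them standing: "Time to progression and duration of response are also endpoints of the study". I found no competing-risk method in the document.

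**The concern.** A patient who dies without progression cannot progress later, so death is a competing event for both endpoints. The plan recognises this for PFS but not for DOR. The same responder, dying without progression, is a failure in the PFS curve and not a failure in the DOR curve.

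For TTP the difficulty is narrower. With deaths censored, Kaplan-Meier describes progression as if nobody could die first. One minus that curve is then presented as an incidence, which it is not.

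Such deaths are plausible here. Section 1.4 puts median survival in stage IV disease below one year. Section 13.4 spaces scans three months apart after day 70, so a patient can deteriorate and die between scans with no documented progression. The DOR analysis may rest on only about 18 responders (the success boundary) to 22 (51% of 44 = 22.4), so a few deaths could move the median. At stake is the accuracy of two published descriptive summaries.

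**Working it through.** The plan states no expected value, sample size or power for DOR or TTP, so it has no figure to reproduce. The check therefore covers direction, then size.

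**Direction**

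- *DOR.* Turning deaths from events into censored observations removes downward steps from the Kaplan-Meier curve, so the curve and its median can only stay or rise. This also holds if dead responders are carried forward to the cutoff date.
- *TTP.* The cumulative incidence adds up the progression hazard times the probability of being alive and progression-free. One minus Kaplan-Meier adds up the same hazard times the probability of being progression-free with death ignored, which is at least as large. It is therefore never below the cumulative incidence.

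**Inputs for size**

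- Median PFS 8.1 and 3.9 months: Figure 8, the two nivolumab plus ipilimumab arms (ipilimumab every 12 and every 6 weeks).
- q, the share of first events that are deaths without progression: assumed 5-30%, not in the documents.
- Median time from response to progression or death: 12 months, assumed for illustration. Figure 8 reports median DOR as not reached.
- Constant cause-specific hazards, with total hazard L = ln 2 / median.

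**Formulas**

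- Planned median, deaths censored at death: (median to progression or death)/(1-q)
- Planned incidence at time t: 1 - exp(-L(1-q)t)
- Cumulative incidence of progression at time t: (1-q)(1 - exp(-Lt))

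**DOR.** 12/0.95 = 12.6, 12/0.90 = 13.3, 12/0.80 = 15.0 and 12/0.70 = 17.1 months.

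The unstated censoring date matters too. In a simulation of 20,000 responders with q = 20% and cutoff 18-36 months after response, the median was 12.0 months with deaths counted, 15.2 with deaths censored at death, and 17.3 with deaths carried to cutoff.

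**TTP at 12 months.** Example for median PFS 8.1 and q = 10%: L = 0.693/8.1 = 0.0856. The planned figure is 1 - exp(-0.0856 x 0.9 x 12) = 60.3%. The cumulative incidence is 0.9 x (1 - exp(-0.0856 x 12)) = 57.8%. All cases (gaps taken before rounding):

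| Median PFS | q | 1-KM, % | Cumulative incidence, % | Gap, points |
|---|---|---|---|---|
| 8.1 | 5% | 62.3 | 61.0 | 1.3 |
| 8.1 | 10% | 60.3 | 57.8 | 2.5 |
| 8.1 | 20% | 56.0 | 51.4 | 4.7 |
| 8.1 | 30% | 51.3 | 44.9 | 6.3 |
| 3.9 | 5% | 86.8 | 83.7 | 3.1 |
| 3.9 | 10% | 85.3 | 79.3 | 6.0 |
| 3.9 | 20% | 81.8 | 70.5 | 11.3 |
| 3.9 | 30% | 77.5 | 61.7 | 15.8 |

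At 24 months the gap grows to 3.0-15.2 points (median 8.1) and 4.6-25.9 points (median 3.9).

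**The case against.** **Censoring deaths is a usual definition of TTP.** This stands. The plan states the start, event and censoring rule, and as a cause-specific measure they are acceptable. What remains is the reading of one minus the curve as an incidence.

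**The TTP rule does not flatter the regimen.** A reader might infer that planned TTP medians are inflated because they exceed PFS medians. TTP and PFS are different endpoints and are meant to differ. Under the same model with q = 10-30%, the planned TTP median is 4.3-5.6 months (PFS 3.9) or 9.0-11.6 months (PFS 8.1), while the cumulative incidence reaches 50% later still, at about 4.6-7.1 or 9.5-14.6 months. Overstating progression works against the treatment.

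**The death share has no source.** This stands as a limit on size. The nearest figures are drug-related deaths of about 1% for ipilimumab and 0.4% for nivolumab (Section 1.3). At 1%, 18-22 responders would give about 0.2 such deaths, and with q = 1-2% a 12-month DOR would become only 12.1-12.2 months (12/0.99, 12/0.98). Deaths from other causes, or between scans, would add to this by an unknown amount.

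**Fatal toxicity would be hidden.** A reader might infer this from the DOR rule, but the documents do not support it. Deaths count in PFS and OS, fatal events are serious adverse events reported within 24 hours (Section 16.1), and the safety board reviews the trial every six months (Section 17.5).

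**A dead responder is counted as still responding.** This also goes beyond the text, which is silent on such a patient. Censoring at death is not the same as continued response.

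**Conclusion.** The point holds in two parts. For DOR, progression is the only event and the handling of death is unstated. Whenever a responder dies without progression during follow-up, the DOR curve lies above one that counts death. The lengthening is about 1/(1-q) if deaths are censored at death, or 5-43% for q = 5-30%, and more if they are carried to cutoff.

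For TTP, the censoring rule can stay as a cause-specific definition, but the curve should not be called an incidence. At 12 months it would overstate progression by about 1-6 or 3-16 points, depending on median PFS.

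The directions follow from the definitions. The sizes rest on constant hazards and an assumed q, and could be small if few patients die before progression. These are secondary, descriptive endpoints in a single-arm trial, with no test or decision attached. The ORR decision and the capture of deaths in PFS, OS and safety reporting are unaffected.

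**What to change.** Amend Section 17.3, Secondary analyses, in about two sentences.

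1. **DOR.** Define it as time from first documented response to documented progression or death from any cause. Censor responders who are alive and progression-free as for PFS, and state the censoring date.
2. **TTP.** Present the incidence of progression with an Aalen-Johansen cumulative incidence function that treats death as a competing event. If Kaplan-Meier is kept, label it as a cause-specific estimate with deaths censored and do not report one minus the curve as an incidence.

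No new data are needed, and the sample size and response-rate rule do not change. The cost is that DOR will look less favourable, by an amount that depends on how many responders die before progression.
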